#### D2.2.3 - Study Protocol for P3-C3-006

Authors: [name], [name], [name], [name], [name]

Version: V4.0

Dissemination level: Public

#### 8.6.3 Other covariates

#### Time of the intervention:

Restrictions for NOMAC were first introduced in 2018, with a transition period from October 2018 to January 2019. Additional EU-level restrictions were implemented in 2020 for products with NOMAC in combination with oestradiol, which were not considered for the study (see limitations for further details).

Regarding the restrictions implemented in 2022, a transition period of three months (November 2022 to January 2023) will be considered to reflect the period during which the intervention was being implemented. This transition period will be applied for all pre- and post-intervention comparisons. For objectives 1 to 5, treatments initiated during this period will be considered for the overall results but not for the stratification by time period (see "Covariates for stratification" below for more information). For objective 6, aggregate monthly figures of this time period will be excluded.

Relevant dates related to the implementation of restrictions in 2018 and 2022 are detailed in Appendix II.

#### **Covariates for stratification:**

Covariates for stratification will vary across objectives and will include:

- Age group:
   10-17, 18-34, 35-49, 50-64, +65 years.
- Indication:

Non-HRT vs. HRT. Indication will be assessed using age as a proxy (non-HRT in women aged 10-49 years, HRT in women aged >50 years).

- Dose:
  - High- vs low- dose, for NOMAC or CMA only. For NOMAC, high doses will include amounts from 3.75mg to 5mg. For CMA, high doses will include amounts from 5mg to 10mg. Low doses will be any amounts less than those specified.
- WHO 5th ATC level codes:
  - For NOMAC or CMA only, if counts allow. For NOMAC codes included will be: G03AA14, G03DB04, G03FB12. For CMA, codes included will be: G03AA15, G03AB07, G03DB06, G03FB03.
- Time period:
  - Preintervention: from start date to October 2022; Postintervention: from February 2023 to study end.

See below which covariates apply according to each objective.

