## Covariates for stratification:

- Age group: 10-17, 18-34, 35-49, 50-64, +65 years (Objective 1)
- Dose: High- vs. low- dose, for NOMAC and CMA only (Objective 1,4,6)
- Indication: HRT (hormonal replacement therapy) vs. non-HRT, with age as a proxy (Objective 1,2,4,6)
- WHO ATC 5th level code: For NOMAC and CMA only (Objective 1 and 5).
- Study period: Pre- vs. Postintervention (Objective 1 to 5).

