#### **Medications of interest:**

#### Drug classes of interest:

- Progestogen and oestrogen combination products not including NOMAC or CMA.
- Progestogens that are pregnadien derivates not including NOMAC or CMA.
- NOMAC (high- and low-dose products, assessed separately)
- CMA (high- and low-dose products, assessed separately)
- Medroxyprogesterone

Drugs used in the management of conditions for which medications of interest might be prescribed:

- Antidepressants
- Antihyperglycemics (Metformin)
- Bisphosphonates
- Clonidine
- Gonadotropin Releasing Hormone antagonists
- Anti-androgens (bicalutamide, flutamide, finasteride, spirolactone, cyproterone acetate)

A preliminary list of concepts to identify pre-specified comorbidities and comedications is detailed in the **Appendix I**. Comorbidities will be measured for any time prior to 1 day before index date, 365 days prior to 1 day before index date and at index date. Concomitant medications will be described 365 days prior to 31 days before index date, and 30 days to 1 day before index date, and at index date.

The operational definition of the covariates is described in the Table 9.

Authors: [name], [name], [name], [name], [name]

Version: V4.0

Dissemination level: Public

**Table 9.** Operational definitions of covariates.

Characteristic	Details	Type of variable	Assessment window	Care Setti ngs 	Code Type	Diagn osis Positi on 	Applied to study populations
Age groups	Defined as: 10-17, 18-34, 35-49, 50-64, +65.	Categorical	N/A	IP, OP	N/A	N/A	General population (objective 1 and 6)
Dose (NOMAC and CMA)	High vs. low doses. For NOMAC, high doses will include amounts from 3.75mg to 5mg. For CMA, high doses will include amounts from 5mg to 10mg. Low doses will be any amounts less than those specified.	Categorical	0	IP, OP	N/A	N/A	General population (objective 1 and 6)
Indication	Non-HRT vs. HRT. Age will be used as a proxy (non-HRT in women aged 10-49 years, HRT in women aged >50 years).	Categorical	0	IP, OP	N/A	N/A	General population (objective 1 and 6)
Comorbidities	Large-scale characterisation and pre-specified conditions 	Binary	[-Inf, -1], [- 365,-1], 0	IP, OP	SNO MED	Any	New users of drug classes or progestogens of interest (objective 3)

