#### Medications of interest:

Medicines of interest will be identified based on ATC 5th and 4th level codes. Some ATC codes incorporate attributes that are not immediately visible (e.g. route, indication, mechanism of action, dosage and combinations). Therefore, not every ATC code containing the name of a drug ingredient is automatically the correct classifier for that drug (i.e. some ingredients show up in more than one ATC code). As an example, medroxyprogesterone is the ingredient of 9 ATC concepts that have the same name but different attributes, such as different indications like those relevant to this study as well as the treatment of neoplastic diseases. In prior vocabulary versions, ATC 5th level concepts were mapped to RxNorm ingredients and, therefore, all those additional attributes were not considered. Although recent efforts have improved the hierarchical structure, some inconsistencies between ATC-RxNorm mapping still exit, especially for combination drugs.(25)

The use of medicines of interest will be derived from prescription data, and therefore assumptions about the use and duration of the drug will be unavoidable (e.g. drug prescriptions do not imply the actual

Authors: [name], [name], [name], [name], [name]

Version: V4.0

Dissemination level: Public

consumption of the medication). In addition, the actual reason for the prescription of the drug is not available in the data and will be assessed using age as a proxy. Age 50 will be used as a threshold to reflect indication, with women older than this age assumed to take this medication for HRT and younger women assumed to take it for non-HRT reasons. This could lead to misclassification, particularly in women who near this threshold age. Misclassification can also occur among women who experience primary ovarian insufficiency (age < 40 years) or early menopause (age 40 to 45), which are estimated to affect 1 to 3% and 5 to 10% of females of high-income countries, respectively.(26)

When assessing the line of treatment (Objective 4), treatment lines will be considered under the assumption that patients receive the treatments of interest for the same indication over time. However, this may not always be accurate, as these treatments can have multiple indications, and patients may be prescribed these medications for different purposes over time.

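### The age proxy for indication leaves women aged exactly 50 in neither the HRT nor the non-HRT stratum (minor wording error)

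*Protocol*

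**What the plan says.** Section 8.6.3 (Covariates for stratification) defines indication by age alone: "non-HRT in women aged 10-49 years, HRT in women aged >50 years". Table 9, which holds the operational definitions of covariates, uses the same cut-points: "Age will be used as a proxy (non-HRT in women aged 10-49 years, HRT in women aged >50 years". Section 11 (Medications of interest) explains that "the actual reason for the prescription of the drug is not available in the data and will be assessed using age as a proxy". It then names 50 as the threshold, with "women older than this age assumed to take this medication for HRT and younger women assumed to take it for non-HRT reasons".

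The age groups in section 8.6.3 are "10-17, 18-34, 35-49, 50-64, +65 years".

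The abstract lists the stratifier as "HRT (hormonal replacement therapy) vs. non-HRT, with age as a proxy (Objective 1,2,4,6", and the objective-by-objective lists in section 8.6.3 agree.

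**The concern.** The non-HRT stratum stops at 49 and the HRT stratum starts above 50. A woman who is 50 has no indication stratum, yet she does have an age group. Indication is a planned stratifier for four of the six objectives: incidence and prevalence, duration and cumulative dose, line of treatment, and the interrupted time series.

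If the code follows the text, a reader who adds the HRT and non-HRT results will not recover the overall result and will find no explanation. The missing year lies at the threshold that the proxy uses to separate the two uses. In Objective 6, treatment starts at age 50 would count in the overall monthly series but in neither indication-specific series.

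**Working it through.** The protocol gives no figure to reproduce here. The check is whether each rule covers every age in completed years.

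**Unit of age.** The age groups run 35-49 and then 50-64. They cover all ages only if age is counted in completed years, so the 10-49 band beside them is read in the same way.

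**Inputs and coverage, ages 10 to 90**

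| Rule | Source | Lower group | Upper group | Ages unassigned |
|---|---|---|---|---|
| Indication | 8.6.3 and Table 9 | 10 to 49 | above 50 | 50 |
| Indication | Section 11 | younger than 50 | older than 50 | 50 |
| Age groups | 8.6.3 | 10-17, 18-34, 35-49 | 50-64, 65+ | none |
| Indication, HRT from 50 | proposed | 10 to 49 | 50 and above | none, and no overlap |

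The gap is exactly one year of age, and the section 11 wording does not close it.

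**Where it acts.** In Objective 1 both the person-time and the new prescriptions at age 50 leave the indication strata. In Objective 2 indication is taken at first use and in Objective 4 at index date, so women starting at 50 leave the strata. Objective 6 models monthly incident counts by indication, so those starts are absent from both series.

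**Possible size.** The protocol gives no age distribution of NOMAC or CMA users. Assuming, for illustration only, that users are spread evenly by year of age, the share lost is 1 / (number of single-year ages in the base):

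- ages 50-64: 1/15 = 6.7%
- ages 45-54: 1/10 = 10.0%
- ages 35-64: 1/30 = 3.3%
- ages 10-64: 1/55 = 1.8%
- ages 10-90: 1/81 = 1.2%

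The range shows that the answer depends on the base chosen. The documents favour none of these bases over another.

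**The case against.** The best defence is that the strict inequality is loose notation. Section 8.5 describes the source population as aged above 10, while section 8.4 starts follow-up on the tenth birthday and the first age group begins at 10. Section 11 calls 50 a threshold, non-HRT ends at 49, and the age groups break between 49 and 50. All of this points to an intended cut at 50 or older, and a programmer might well code it so. The defence stands as to intent and keeps the point minor. It does not remove the point, because the operational table states the rule with a gap and section 11 repeats the gap in words.

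A reader might go further and infer that age overrides what the product code already shows, so that known contraceptive and HRT combinations are misclassified and should be reclassified by ATC code. The documents do not support this:

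- The protocol never labels the NOMAC or CMA codes as contraceptive or HRT, and it has no code-based indication rule to be overridden. Section 6 says that approved indications differ by strength and country.
- The statement in section 11 that "Some ATC codes incorporate attributes that are not immediately visible (e.g. route, indication, mechanism of action, dosage and combinations" is a caution about relying on codes. The same paragraph warns of remaining ATC-RxNorm inconsistencies, especially for combination products.
- The proxy is deliberate, and section 11 discloses misclassification near the threshold and in ovarian insufficiency or early menopause.
- Objective 1 reports rates per person-time. Age can define both numerator and denominator, but a product code cannot, because women who are not users have none.

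**Conclusion.** The point holds as a minor error in a stated rule. As written, age 50 belongs to neither indication stratum, so the strata of Objectives 1, 2, 4 and 6 are not exhaustive and disagree with the age groups. This rests on counting age in completed years and on the rule being applied literally.

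The number of women affected cannot be derived from the protocol. The 6.7% of the 50-64 band is an illustration under flat use. A reader might expect a much larger share by supposing that use falls steeply after 50, but the documents give no age pattern to support that. Unstratified results do not change.

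**What to change.** Define HRT as age 50 years or older, and non-HRT as 10 to 49 years, in section 8.6.3, in Table 9 and in the limitations text of section 11. The indication strata then sum to the total, and the cut coincides with the 35-49 / 50-64 boundary.

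The change is to wording and one comparison operator, with no new data and no change to the design. It is cheapest before the code is run. Each data partner executes the code locally and returns only aggregates, so a literal implementation found later would generally need a rerun at the three sites. If the sponsor does intend to leave out age 50, the protocol should say so and report how many women it excludes.

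No reclassification by product code is needed for this correction.

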#### Objective 1:

Drug classes and progestogens of interest will be assessed separately ("8.6. Variables"). Covariates for stratification will include:

- Age group
- Indication
- Dose
- WHO 5th ATC level codes
- Time period

#### Objective 2:

NOMAC and CMA will be assessed separately. Covariates for stratification will include:

- Indication
- Time period

Authors: [name], [name], [name], [name], [name]

Version: V4.0

Dissemination level: Public

#### Objective 3:

Drug classes of interest will be described as part of the characterisation (see "Covariates for Objective 3" for more information).

- Time period

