#### **Exposures**

- Objective 1: N/A
- Objective 2, 4 and 5: First-ever prescription of NOMAC or CMA (assessed separately)
- Objective 3: First-ever prescription of NOMAC or CMA (assessed separately)
- Objective 6: N/A

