## 8.4 Follow-up

For the population-level DUS (objective 1), study participants in the denominator population will start contributing person time on the latest of the following: 1) study start date (1st January 2010, or as defined according to the database), 2) date on which they turn 10 years old, 3) date at which they have a year of prior history recorded. Participants will stop contributing person time at the earliest date of the following: 1) end of available data in each of the data sources, 2) date at which their observation period ends (e.g. loss to follow-up, death).

For the patient-level DUS (objective 2 to 5), participants will be followed up from the day of incident prescription of medication (index date), until the earliest end of data availability, date at which their observation period ends (e.g. loss to follow-up, death), or 180 days after ending treatment (objective 5). For objective 2, 4 and 5, index date will be defined as the date of the first-ever prescription of NOMAC or CMA. For objective 3, this will be defined as the date of the first-ever prescription of any of the 6 drug classes of interest (see "8.6.2 Outcomes").

For objective 4, line of treatment will be assessed retrospectively by looking at prior records of alternative treatments, from the date of initiation of treatment with products containing NOMAC or CMA to start of the study period (1st January 2010, or as defined according to the database).

For objective 6, follow-up will be the same as that for objective 1.

Information on the operational definition of index date is described in **Table 4**. Please note that, for objectives 1 and 6, each drug class of interest will be assessed separately, with the washout window specific to the drug class being studied (e.g., when studying NOMAC, the washout window will be applied with respect to this substance only). For objective 3, the washout will be applied to all the drug classes of interest combined.

Authors: [name], [name], [name], [name], [name]

Version: V4.0

**Dissemination level:** Public

Table 4. Operational definition of time 0 (index date) and other primary time anchors.

Study population names	Time Anchor Description (e.g. time 0) 	Number of entries 	Type of entry	Washout window	Care Setting 	Code Type 	Incident with respect to

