General population (objective 1 and 6)	Study entry date	Multiple entry	Incident , prevale nt	[-365, -1]	IP, OP	N/A	Outcome drug class (assessed separately)
Patients with prior history of meningioma (objective 1, subgroup analysis)	Date of diagnosis	Single entry	Incident	[-Inf, 0]	IP, OP	SNOME D	Meningiom a
New users of NOMAC (objective 2, 4 and 5)	Date of prescription	Single entry	Incident	[-Inf, -1]	IP, OP	RxNorm	NOMAC
New users of CMA (objective 2, 4 and 5)	Date of prescription	Single entry	Incident	[-Inf, -1]	IP, OP	RxNorm	СМА
New users of drug classes or progestogens of interest (objective 3)	Date of prescription	Single entry	Incident	[-Inf, -1]	IP, OP	RxNorm , SNOME D	Drug classes of interest (any)

¹ Study entry date (objective 1 and 6) will be defined as the latest of the following: 1) study start date (1st January 2010, or as defined according to the database), 2) date on which they turn 10 years old, 3) date at which they have a year of prior history recorded.

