## **Table 7.** Operational definitions of exposure.

Exposure group names 	Details	Washout window	Assessment Window	Care Setting 	Code Type 	Applied to study populations	Incident with respect to
Drug classes of interest (any)	To characterise users of any of the drug classes or progestogens of interest(objective 3). Consisting of first-ever prescription to any of the drug classes or progestogens of interest (see "8.6 Variables").	[-Inf, -1]	0	IP, OP	RxNorm	New users of drug classes or progestogens of interest (objective 3)	Drug classes or progestogens of interest (any)
NOMAC	First-ever prescription to NOMAC. To identify study participants exposed to the drug for objective 2, 4 and 5.	[-Inf, -1]	0	IP, OP	RxNorm	New users of NOMAC (objective 2, 4 and 5)  New users of CMA (objective 2, 4 and 5)	NOMAC
CMA	First-ever prescription to CMA.	[-Inf, -1]	0	IP, OP	RxNorm	New users of NOMAC (objective 2, 4 and 5)  New users of CMA (objective 2, 4 and 5)	CMA

<sup>1 NOMAC = nomegestrol, CMA = chlormadinone

<sup>2 IP = inpatient, OP = outpatient, ED = emergency department, OT = other, n/a = not applicable

<sup>3 RxNorm codes will be identified based on the vocabulary hierarchy, with ATC codes being ancestors.

Authors: [name], [name], [name], [name], [name] Version: V4.0

**Dissemination level:** Public

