#### Objective 3:

Characteristics will be described by means of large-scale characterisation. The top 10 of disease codes and top 10 of drug codes will be described in the report to simplify dissemination. Pre-specified comorbidities and concomitant medications will also be reported within specific time windows (see "8.6.3. Other covariates"). The number of patients initiating high- or low-doses of NOMAC and CMA (assessed separately) and the number of years since meningioma diagnosis will also be described.

Results will be reported overall and stratified by study period (pre- vs. postintervention).

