#### A. Primary analysis

Hypothesis:	Objective 1: Not applicable, descriptive analysis.
	Objective 2: Cumulative dose and duration of treatments with NOMAC or CMA will be lower after the implementation of restrictions.
	Objective 3: The number of new users of NOMAC or CMA with prior history of meningioma will be reduced after the implementation of restrictions.
	Objective 4: The number of users initiating NOMAC or CMA as first-line treatment will be reduced after the implementation of restrictions.
	Objective 5: The number of discontinuations and switches from NOMAC or CMA to other drug classes will increase after the implementation of restrictions.
	Objective 6: The incidence of NOMAC or CMA will be reduced after the implementation of restrictions, especially for high-dose products. This reduction will not be observed for other drug classes of interest.
Exposure contrast:	Objective 1: Not applicable, descriptive analysis.
	Objective 2: Pre-intervention (1-year period) vs. Post-intervention (1-year period)
	Objective 3 to 6: Pre-intervention vs. Post-intervention
Outcome:	Objective 1: Incidence rates and prevalence of drug classes of interest
	Objective 2: Cumulative dose and treatment duration of NOMAC or CMA.

Authors: [name], [name], [name], [name], [name]

Version: V4.0

Dissemination level: Public

	Objective 3: Number and characteristics of users of drug classes of interest.
	Objective 4: Line of treatment when initiating NOMAC or CMA.
	Objective 5: Diagnosis with meningioma during treatment. Discontinuations and switches
	from treatments with NOMAC or CMA to others.
	Objective 6: Incidence rates of NOMAC or CMA.
	Drug classes of interest, NOMAC and CMA will be assessed separately.
Analytic software:	R
Model(s):	Objective 1: Not applicable, descriptive analysis.
	Objective 2 to 5: Standardised mean differences.
	Objective 6: Segmented regression (Poisson models).
Confounding adjustment method	
	Stratification.
Missing data methods	
	The absence of a record for a condition or medication will be considered as the absence of the disease or use of the medication.
Subgroup Analyses	
	Objective 1: Age groups, indication, study period. For NOMAC or CMA only: dose, WHO ATC 5 th level (if counts allow). A subgroup analysis will be performed restricting the study population to individuals with a prior history of meningioma.
	Objective 2: Study population, indication, study period.
	Objective 3: Study period.

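### Objective 3 is defined inconsistently: the operational text pools starters of any study class, which would dilute the meningioma-history comparison that Table 11 poses for NOMAC and CMA

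*Protocol*

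**What the plan says.** **Text that pools.**
- Section 8.4: "For objective 3, the washout will be applied to all the drug classes of interest combined". Table 4 has one population row for this objective, "New users of drug classes or progestogens of interest (objective 3"), with single entry and incidence judged against any class. Table 6 excludes women with earlier use of any class.
- Table 7: the exposure group is "Consisting of first-ever prescription to any of the drug classes or progestogens of interest". Appendix I gives Objective 3 one concept set covering G03AA, G03AB, G03DB, G03FA and G03FB.
- Section 8.6.3, Objective 3: "Drug classes of interest will be described as part of the characterisation", then time period alone. The entries for the other five objectives each state that the drugs are assessed separately.
- Section 8.8, Objective 3: "Results will be reported overall and stratified by study period (pre- vs. postintervention"). The SMD text for Objectives 2 to 5 restricts the patient-characteristic comparison to conditions recorded at any time before index.
- The abstract's population entry and the exposure row of Table 1 also say any class.

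**Text that separates.**
- Abstract, Exposures: "Objective 3: First-ever prescription of NOMAC or CMA (assessed separately").
- Table 11, outcome row: after the outcomes of all six objectives, a general line says that the drug classes, NOMAC and CMA are assessed separately.

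**Hypothesis.** Table 11: "The number of new users of NOMAC or CMA with prior history of meningioma will be reduced after the implementation of restrictions". Table 1 words the Objective 3 hypothesis differently, as fewer NOMAC or CMA new users, without mention of meningioma.

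**The concern.** The 2022 contraindication for women with current or past meningioma applies to products containing NOMAC or CMA. The Table 11 hypothesis therefore concerns starters of those two substances. A cohort of all starters of combined contraceptives, HRT combinations and pregnadien derivatives, split only into before and after, does not isolate them. The index product would be one descriptive row of the table. No planned Objective 3 output crosses it with meningioma history.

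Two errors of reading could follow. A real fall among NOMAC/CMA starters could be lost among starters of unrestricted products. A change in product mix could shift the pooled figure and be taken as an effect of the measures, because section 8.8 presents these SMDs as the measure of impact on the user profile.

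**Working it through.** The protocol gives no SMD, sample size or expected prevalence for Objective 3, so there is no stated figure to reproduce. The check shows how a change confined to NOMAC/CMA starters appears in the pooled cohort.

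**Inputs (all assumed; the documents give none).**
- p: pre-period prevalence of meningioma history, equal in all starters, 0.05% to 0.5%.
- w: NOMAC/CMA share of all starters, 2% to 50%.
- r: true relative reduction among NOMAC/CMA starters, 100% or 50%.

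**Formulas.**
- SMD = (p₀ − p₁) / √{[p₀(1 − p₀) + p₁(1 − p₁)] / 2}.
- Within NOMAC/CMA: p₁ = p(1 − r).
- Pooled: p₁ = w·p(1 − r) + (1 − w)·p = p(1 − w·r). The pooled relative fall is therefore w·r.

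**Worked case, p = 0.05%, r = 100%, w = 10%.**
- Within NOMAC/CMA: 0.0005 / √(0.0005 × 0.9995 / 2) = 0.0316.
- Pooled: p₁ = 0.00045, and 0.00005 / √[(0.0005 × 0.9995 + 0.00045 × 0.99955) / 2] = 0.0023.

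**SMD over the range.**

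| p | r | Within NOMAC/CMA | Pooled, w = 2% | w = 10% | w = 25% | w = 50% |
|---|---|---|---|---|---|---|
| 0.05% | 100% | 0.0316 | 0.0004 | 0.0023 | 0.0060 | 0.0129 |
| 0.1% | 100% | 0.0447 | 0.0006 | 0.0032 | 0.0085 | 0.0183 |
| 0.1% | 50% | 0.0183 | 0.0003 | 0.0016 | 0.0041 | 0.0085 |
| 0.5% | 100% | 0.1003 | 0.0014 | 0.0073 | 0.0189 | 0.0409 |

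At a 10% share, full elimination appears as a 10% relative fall, and the SMD is about 14 times smaller (0.1003 / 0.0073 = 13.7). At a 50% share it is about 2.5 times smaller (0.1003 / 0.0409 = 2.45). Under full elimination the SMD shrinks somewhat more than the share alone implies, because a zero post-period proportion also reduces the denominator of the unpooled SMD.

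**Product mix alone.** Take a history prevalence of 0.2% in NOMAC/CMA starters and 0.05% in others, unchanged over time, and a NOMAC/CMA share falling from 25% to 15%.
- Before: 0.25 × 0.2% + 0.75 × 0.05% = 0.0875%.
- After: 0.15 × 0.2% + 0.85 × 0.05% = 0.0725%.
- Relative change: 0.0725 / 0.0875 − 1 = −17%, with no change among NOMAC/CMA starters.

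With the two prevalences exchanged, the pooled figure goes from 0.1625% to 0.1775%, a rise of 9%.

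**Redirection.** If women with a history start another study class instead of NOMAC or CMA, they stay in the pooled cohort and its prevalence does not change.

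**The case against.** A reader might infer that the protocol settles on pooling and so cannot show whether prescribing to women with meningioma has changed. The documents do not support that, for these reasons.

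- The abstract's exposure list and the general line in Table 11 both say separate assessment. The protocol contradicts itself; it does not plainly choose the pooled analysis.
- Objective 1 has a subgroup of women with a history of meningioma in which NOMAC and CMA are separate outcomes. It bears on the contraindication without dilution by women who have no history. It is descriptive, however, is reported only overall and by calendar year, and is not the Objective 3 comparison.
- The Table 1 hypothesis, fewer NOMAC or CMA new users, is partly served by the planned Objective 3 counts of high- and low-dose NOMAC and CMA starters. Those counts are not crossed with meningioma history, and in this cohort they cover only women without prior use of any study class.
- An any-class cohort fits the objective's general aim of describing users of the relevant classes.
- Rarity limits this comparison in any case. Section 11 puts meningioma counts in the hundreds in most databases and calls an effect analysis in that population infeasible. Even full elimination gives an unpooled SMD of only 0.03 to 0.10 over the assumed range.

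All of this limits the reach of the point. It leaves standing the conflict between the operational text and the Table 11 hypothesis, and the dilution that follows from the operational text.

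**Conclusion.** The point holds as an inconsistency with a quantifiable consequence. Someone programming from sections 8.4 to 8.8 and Appendix I would produce one any-class cohort split by period. Its meningioma-history SMD would not answer the Table 11 hypothesis.

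If history prevalence is equal across starters, the pooled relative change is the NOMAC/CMA change multiplied by the NOMAC/CMA share. That result does not depend on the prevalence chosen. The sizes do rest on assumptions: with full elimination, prevalence of 0.05% to 0.5% and a 10% share, the SMD is about 0.03 to 0.10 within NOMAC/CMA and about 0.002 to 0.007 pooled. The true share and prevalence are not in the protocol.

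It is also tempting to conclude that adding the index product as a stratum of the existing cohort would repair this. It would not. The combined washout has already removed NOMAC and CMA starters who had earlier used another study class, so the strata would not represent all NOMAC or CMA starters.

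**What to change.** - In sections 8.6.3 and 8.8, report meningioma-history counts, proportions and pre/post SMDs for Objective 3 separately in the NOMAC and CMA new-user cohorts that Table 4 already defines for Objectives 2, 4 and 5. Their washout is specific to each substance.
- Keep the pooled any-class characterisation as the descriptive table, and state that it is not the test of the Table 11 hypothesis.
- Align the abstract (Population and Exposures), the Table 1 and Table 11 hypotheses, section 8.6.3, section 8.8 and the general line in Table 11, so that each gives the same cohort and the same hypothesis.

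The cost is small, because the cohorts and the condition codes already exist. There will be more tables, and some meningioma cells will be suppressed under the minimum count of 5. The report should say that separation removes the dilution but leaves few women with a history, so the SMDs will stay small and imprecise.
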